For Aim 3, the analysis will use non-inferiority testing to compare mental health and QOL across ATTOC and UC at weeks 36 and 52. Standard statistical tests, which may yield a non-significant comparison of means or proportions, cannot be used to claim that the treatments are equal since "the absence of evidence is not evidence of absence". Among persons with SMI, the rate of psychiatric hospitalization nationally is 11.4% [114], which may represent UC (i.e., 88.6% of UC subjects will not have a hospitalization across the 52 weeks). One study found that 3.3% of clients with an SMI treated for TUD had a psychiatric hospitalization [48] or that 96.7% of clients treated for TUD did not experience a psychiatric hospitalization. We assume 14 sites (700 clients), with potential loss of 15% to follow-up, and assume approximately 90% non-hospitalization in the UC group. We will set our non-inferiority floor 20% below the US rate, which yields 80% power to detect non-inferiority if the ICC is as much as 0.15 (more power if ICC is less than 0.015).

A trial with smokers with an SMI reported baseline BASIS-R scores of 2.1 (SD=0.8) and SF-12 scores of 48.7 (SD=12.5) for the physical sub-scale and 27.8 (SD=12.9) for the mental sub-scale, which estimates UC [107]. Given the sample of 14 sites (700

clients) and potential 15% loss to follow-up, we have 80% power ($\alpha=0.05$) to detect non-inferiority if the results for the ATTOC arm differ from UC by as much as 0.19 on the BASIS-R, when ICC=0, and by 0.50 when ICC=0.15.

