The effects of the ATTOC model on client mental health functioning and QOL: We will compare treatment arms in terms of the frequency of hospitalizations (binary) and mental functioning evaluations (continuous) over 52 weeks. Again, we will use mixed models to account for clustering, while accommodating either the binary outcome with logistic regression or the continuous measures with linear regression. Equivalence uses two one-sided tests against lower and upper equivalence bounds. The null hypothesis is that the groups are not equivalent and are determined to be equivalent when the mean or proportion is significantly different from both boundaries. We will use this approach to determine whether hospitalization rates are higher (null) in the ATTOC group or equivalent, and whether mental functioning is lower in the ATTOC group (the null) or equivalent. All hypotheses will be tested at $\alpha=0.05$ (0.025 for any one sided non-inferiority test).

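### Aim 3 is powered as one-sided non-inferiority but analysed by a two-boundary rule with no upper bound, and BASIS-R and SF-12 have no fixed margin

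*Combined protocol and SAP*

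**What the plan says.** Section 3.1 frames Aim 3 as a non-inferiority hypothesis on mental health functioning and quality of life. Section 7.1 agrees: "the analysis will use non-inferiority testing to compare mental health and QOL across ATTOC and UC at weeks 36 and 52".

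Section 7.2.1 introduces equivalence by two one-sided tests against a lower and an upper bound, with the arms "determined to be equivalent when the mean or proportion is significantly different from both boundaries". It continues: "We will use this approach to determine whether hospitalization rates are higher (null) in the ATTOC group or equivalent", and does the same for lower mental functioning. It closes with a level of "0.025 for any one sided non-inferiority test".

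The margin information is all in section 7.1:

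- **Hospitalisation:** "We will set our non-inferiority floor 20% below the US rate", with about 90% non-hospitalised assumed in usual care and 80% power claimed for an ICC up to 0.15.
- **BASIS-R:** 80% power for non-inferiority if the arms "differ from UC by as much as 0.19 on the BASIS-R, when ICC=0, and by 0.50 when ICC=0.15".
- **SF-12:** "SF-12 scores of 48.7 (SD=12.5) for the physical sub-scale and 27.8 (SD=12.9) for the mental sub-scale". No margin, detectable difference or power follows.

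**The concern.** There are two separate gaps.

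**The test.** A rule that needs significance against two boundaries cannot be carried out when only one boundary exists, and then for only one outcome. It is also not the test that section 7.1 powers. An analyst following section 7.2.1 literally would have to invent a bound.

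**The margins.** The BASIS-R figures are what the sample can detect at two assumed ICCs. If they serve as the margin, the criterion depends on an ICC that is known only after the data are in. For SF-12 there is nothing to test against. In both cases the margin could be chosen once results are visible, and for BASIS-R that choice can decide the conclusion.

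**Working it through.** **Inputs (section 7.1, with the 7:7 allocation from section 4.1).** 700 clients in 14 clinics with 15% loss leaves 595, that is 297.5 per arm and 42.5 per clinic. SDs: BASIS-R 0.8, SF-12 physical 12.5, SF-12 mental 12.9. One-sided level 0.025 (section 7.2.1).

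**Formulas.** Design effect DE = 1 + 41.5 × ICC. For a mean, SE = SD × √(2 × DE / 297.5). Difference with 80% power = (1.96 + 0.84) × SE = 2.80 × SE. Power for margin M with no true difference = Φ(M/SE − 1.96).

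**1. Reproducing the plan's BASIS-R figures.**

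| ICC | DE | SE | 2.80 × SE | Plan |
|---|---|---|---|---|
| 0 | 1 | 0.0656 | 0.184 | 0.19 |
| 0.15 | 7.225 | 0.1763 | 0.494 | 0.50 |

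Both agree after rounding up, so the stated figures are those of a one-sided 0.025 non-inferiority test. In SD units they run from 0.19/0.8 = 0.24 to 0.50/0.8 = 0.63.

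**2. One data set, two answers.** At ICC 0.05, DE = 3.075 and SE = 0.1150. With zero observed difference the harm-side limit is 1.96 × 0.1150 = 0.225 by z, or 2.179 × 0.1150 = 0.251 by t on 12 df (14 clinics less 2). Either limit lies inside 0.50 and outside 0.19.

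**3. Power if either figure became the fixed BASIS-R margin (z).**

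| Margin | ICC 0 | ICC 0.05 | ICC 0.15 |
|---|---|---|---|
| 0.19 | 83% | 38% | 19% |
| 0.50 | >99% | 99% | 81% |

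**4. SF-12, which the plan leaves blank.** Differences with 80% power (z):

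| Sub-scale | ICC 0 | ICC 0.15 |
|---|---|---|
| Physical | 2.9 | 7.7 |
| Mental | 3.0 | 8.0 |

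These show what the sample could support. They are not proposed margins.

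**5. Hospitalisation floor.** The national non-hospitalisation rate in section 7.1 is 88.6%. A relative reading gives 0.8 × 88.6 = 70.9%; an absolute reading gives 88.6 − 20 = 68.6%. With 90% in both arms and ICC 0.15, SE = √(2 × 0.9 × 0.1 × 7.225 / 297.5) = 0.0661.

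- Relative: Φ((0.900 − 0.709)/0.0661 − 1.96) = 82%.
- Absolute: Φ((0.900 − 0.686)/0.0661 − 1.96) = 90%.

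Both are at or above the claimed 80%, so the power statement cannot identify the floor. In hospitalised terms the floors are 29.1% and 31.4%, against 11.4% nationally.

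**The case against.** The strongest reply is that section 7.2.1 is only loosely worded. Its two-test sentences can be read as a general account of equivalence testing; the sentence that applies it names harm-direction nulls only, a one-sided 0.025 level follows, and the power figures fit that test. This is a fair reading of the intent, and it is why the fix keeps non-inferiority. It does not remove the conflict in the text, and it supplies no margin for BASIS-R or SF-12.

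Four stronger readings may tempt a reader, and the documents do not support them.

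- **That Aim 3 has no usable rule for any outcome.** Hospitalisation has a floor, stated power, a null direction and a level. It lacks only a precise definition of the floor. Quality of life does have a hypothesis, in section 3.1; what it lacks is a margin.
- **That the two-boundary rule would cost a known amount of power, or would fail ATTOC for benefit.** Either needs an upper bound that the plan never sets. Mirroring the 20-point floor on 88.6% would put it at 108.6%, which is impossible.
- **That the floor must mean percentage points.** Step 5 shows that the relative reading also meets the stated power, and lies closer to 80%.
- **That "mental functioning evaluations (continuous) over 52 weeks" contradicts testing at weeks 36 and 52.** It can simply describe the follow-up period, and section 7.1 itself counts hospitalisation across the 52 weeks.

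On the arithmetic, the t version is my choice: the only reference distribution the plan names is a z-score, for Aim 1. The SEs use unadjusted baseline SDs; baseline adjustment in the mixed model could reduce them.

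**Conclusion.** The concern holds, and it needs correcting before outcome data are seen. The decision rule written for Aim 3 is not the test that was powered and cannot be carried out as written. BASIS-R has two ICC-dependent detectable differences in place of a margin, more than 2.5-fold apart (0.50/0.19), and a null result at a moderate ICC passes one and fails the other. SF-12 has no criterion at all.

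Hospitalisation is a lesser problem of definition. Under either reading of the floor, success excludes only a rise to about 29–31% hospitalised, which is a weaker statement than the section 3.1 hypothesis of no significant degradation.

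The figures assume 15% loss, equal clinic sizes, the plan's SDs and no true difference between arms. The ICC is unknown, so the plan's own range of 0 to 0.15 is used. The power arithmetic in section 7.1 is not in error.

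**What to change.** **Section 7.2.1.** Replace the two-boundary rule with the test that was powered: for each Aim 3 outcome, conclude non-inferiority if the harm-side 97.5% confidence limit for ATTOC versus usual care lies inside the margin (one-sided 0.025).

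**Section 7.1, before outcome data are seen.** The sponsor should:

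- fix one margin that does not depend on the ICC for BASIS-R and for each of the two SF-12 sub-scales, give a rationale, and state power across the ICC range;
- state whether the hospitalisation floor is relative or absolute, and whether it is a fixed level or a between-arm difference;
- test that floor on the proportion scale, since the planned mixed logistic model yields an odds ratio and the plan does not say how that is compared with a floor on a proportion.

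Word the hospitalisation conclusion as the size of rise ruled out.

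**Cost.** Text only, with no extra participants. Removing a boundary that was never set loses no power. The real cost is candour: once margins are fixed, stated power for BASIS-R or SF-12 may fall below 80% at higher ICCs.

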Client/Personnel Eligibility Screen		X											
TREATMENT													
ATTOC			X	X	X	X	X	X	X	X	X	X	
UC			X ²										
MEASURES													
COVARIATES													
Demographics, Smoking History & FTND (S-KAP, S-KAS)		X				X			X			X	X
Client Psychiatric History ²		X											
Client COVID-19 Questionnaire		X											
Clinic/Clinician Change (The Dashboard)			X	X	X	X	X	X	X	X	X	X	
MEDIATORS													
Personnel Knowledge and Attitudes (S-KAP)		X				X			X			X	X
Client Knowledge and Attitudes (S-KAS)		X				X			X			X	X
TREATMENT DATA													
ATTOC Intervention Adherence (The Dashboard)			X	X	X	X	X	X	X	X	X	X	
ATTOC Change Plan			X			X							
ATTOC Environmental Scan			X			X							
ATTOC Communication Plan			X			X							
OUTCOMES													
Adherence to TUD Guidelines (S-KAP)		X				X			X			X	X
Adherence to TUD Guidelines (S-KAS)		X				X			X			X	X
Adherence to TUD Guidelines (Client Prescription Data) ²												X	X
Client Smoking Status (CO Form)		X											
Client Smoking Status (TLFB)						X			X			X	X
Client Mental Health (BASIS-R)		X				X			X			X	X
Client QOL (SF-12)		X				X			X			X	X
Client Hospitalization Form ²												X	X
Treatment and Client Costs		X										X	X

¹ Activities associated with this timepoint may occur any time within the 4-6 week period directly preceding Week 1.

² Data provided by request from Community Behavioral Health (CBH)

³ This is a one-day training lead by [name] and/or [name].

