6.1.1 Baseline

Eligible and interested client and clinic personnel participants will complete informed consent and HIPAA documents and baseline assessments. Following receipt of informed consent and HIPAA authorization, a baseline assessment will be completed. The baseline assessments will collect a broad range of data, including demographics and smoking history for both participant groups and psychiatric history data for client participants. Client participants will also complete a smoking status review (CO Form), the BASIS-R, SF-12 and a hospitalization assessment. Additionally, personnel participants will complete the Smoking Knowledge, Attitudes, and Practices (S-KAP) survey and client participants will complete the Smoking Knowledge, Attitudes, and Services (S-KAS) survey. [105]. At UC clinics, baseline assessments help ensure that any differences across UC sites at baseline can be controlled for in subsequent analyses. Compensation for the baseline session will be distributed when baseline questionnaires have been completed. For those participants (either personnel or clients) who complete the informed consent and HIPAA documents, but cannot complete the baseline assessments until a later date, payment will be deferred until baseline questionnaires have been completed. An appointment will be made with the participant to ensure that all session questionnaires are completed and compensation provided.

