Usual Care (UC): No study procedures will be performed at Weeks 16, 20, 28, or 32. At Week 24, clinic personnel will complete the S-KAP and clients will complete the S-KAS, BASIS-R, and SF-12. At Week 36 (EOT) and 52, clinic personnel will complete the S-KAP and clients will complete the S-KAS, BASIS-R, SF-12, hospitalization assessment and smoking status review (self-reported TLFB and CO reading). Treatment and client costs will also be assessed as one of the outcomes variables measured at Week 36 and 52.

ATTOC Intervention: Sessions spanning weeks 16 through 36 are provided via video-conference (or teleconference) to assess dashboard data, reinforce training initiated in past sessions, and address concerns or obstacles that emerged during implementation. Formal performance feedback (based on dashboard data) to the clinics is again provided. Updated policies and SOPs are given to staff (step 9). These “booster” sessions to continue performance feedback promote sustainability of organizational change (step 10).

Assessments will occur at weeks 12 and 24 to facilitate the performance feedback (e.g., clinical practices, barriers, client smoking) and to allow for exploratory mediation analyses using the S-KAP and S-KAS surveys. These ~30 minute assessments will be conducted in person at the sites by the trained study staff.

At Week 24, clinic personnel will complete the S-KAP and clients will complete the S-KAS, BASIS-R, and SF-12. At Week 36 (EOT) and 52, clinic personnel will complete the S-KAP and clients will complete the S-KAS, BASIS-R, SF-12, hospitalization assessment and smoking status review (self-reported TLFB and CO reading). Treatment and client costs will also be assessed as one of the outcomes variables measured at Week 36 and 52.

At Week 36 (EOT), ATTOC clinics will be congratulated on completing the program with certificates of completion. Both individuals participating as personnel, in addition to the clinic as a whole, will be awarded these certificates. Clinic personnel will be notified that they will be able to contact [name] with any follow-up questions or concerns. In addition, ATTOC clinics will be given the option of receiving information about other area ATTOC clinics, to allow for communication and collaboration between them.

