The cost-effectiveness of the ATTOC program vs. UC: We will compare the societal cost (i.e., the sum of all measured categories of costs, including treatment and indirect costs) and effects of ATTOC vs. UC. If one treatment is found to be more costly and more effective, there is a trade-off between the additional effectiveness and additional resources needed to achieve those outcomes. This trade-off is represented by the incremental cost-effectiveness ratio (ICER), which is a ratio of the difference between mean costs in each treatment group and the difference between the cessation rates across treatment arms at weeks 36 and 52. This ratio will represent the additional cost of ATTOC vs. UC to produce an additional quitter. The quit rate outcome measure is used in our primary measure of cost-effectiveness because it is measured directly and because it can be compared against economic evaluations of other smoking interventions. Hypothesis testing for an ICER involves determining whether the ICER is significantly $<$ the maximum acceptable ICER. Unfortunately, the maximum willingness to pay for a quit is unknown. However, \$50,000 is accepted as a maximum ICER for the outcome of cost/life year saved, but wide bands around this value are common. This outcome looks at cost-effectiveness of the intervention over a lifetime. Because this is a relatively brief trial we will use a simulation-based analysis to project effects of quitting into long-term mortality and costs [116], employing standard assumptions and parameters [117]. Because this projection is based on parameters that have wide ranges, we will conduct a sensitivity analysis to assess the sensitivity of our estimates of costs and cost-effectiveness to the speculative nature of some of the values used in the analysis. We will consider how cost-effectiveness may change with different: 1) costs of treatment; 2) methods to handle attrition of cost data; and 3) ceiling ratios. Because of the poor statistical properties of the ICER as with ratios [118], we will transform the ratio into incremental net monetary benefits (INMB) with the following: $[L \cdot E] - C$ where L =ceiling ratio, E =difference in mean effects, and C =difference in mean costs. The hypothesis test that the ICER is $<$ the ceiling ratio is equivalent to the hypothesis test that the INMB is >0 . The INMB standard error is estimated with the formula in Willan [119] and amounts to the typical statistical formula for standard error. The hypothesis is that the ICER will be cost effective if the

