
INMB expression of cost/life year saved is >0 at an $\alpha < 0.05$. We will also judge the cost-effectiveness ratio as being acceptable if the confidence interval for the INMB excludes 0.

Exploratory Aims: The effects of treatment arm on potential mediators (barriers) will be assessed using linear regression-based structural equation modeling (SEM). It is hypothesized that treatment arm will yield significant differences in proposed mediators which will predict week 36 and 52 quit rates and adherence to treatment guidelines. We will examine changes in mediators from baseline to week 8. After first demonstrating that treatment arm affects adherence and quit rates (Aims 1 and 2), these effects will be partitioned into mediated and unmediated effects, via path analysis and SEM. Specific hypotheses will be tested by using chi-square difference tests that contrast the overall fit of this full model with more parsimonious nested models in which specific predictive effects are fixed to zero (e.g., an unmediated path). Model goodness-of-fit indices will be contrasted to guide interpretation of results and determine the practical significance of statistically significant differences. Modification indices will be examined to guide model interpretation and modification and binary and continuous variables can be handled by Stata. This approach allows us, in principle, to test whether treatment effects on Aim 1 and 2 outcomes are due to specific mechanisms (e.g., reduction in barriers).

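### The INMB cost term is an unadjusted difference in mean costs with an ordinary standard error, although the schedule marks client costs at baseline and whole clinics are randomised

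*Combined protocol and SAP*

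**What the plan says.** Section 7.2.1 (cost-effectiveness) defines the INMB as the ceiling ratio times E, minus C, where E and C are "difference in mean effects, and C =difference in mean costs". The standard error is said to be one that "amounts to the typical statistical formula for standard error". The ceiling is $50,000, which "is accepted as a maximum ICER for the outcome of cost/life year saved".

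The verdict rests on this quantity: the intervention is cost-effective if the "INMB expression of cost/life year saved is >0 at an" alpha below 0.05, and "We will also judge the cost-effectiveness ratio as being acceptable if the confidence interval for the INMB excludes 0". The planned sensitivity analyses vary treatment costs, the handling of missing cost data and the ceiling ratio.

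The documents differ on when costs are collected:
- The schedule table in section 6 has a row "Treatment and Client Costs" marked at Baseline, Week 36 and Week 52.
- Section 6.1.1 lists the client baseline assessments without costs.
- Section 6.2.5 says "Treatment and client costs will also be assessed as one of the outcomes variables measured at Week 36 and 52".

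Two general statements bear on adjustment. Section 6.1.1 says the baseline assessments help ensure that "any differences across UC sites at baseline can be controlled for in subsequent analyses". Section 7.2 allows variables related to arm or to follow-up completion at p < .10 as optional covariates, and says clustering will be handled with mixed models. The INMB paragraph applies neither.

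**The concern.** C sums all measured costs, including medical services outside the study (sections 4.7 and 4.8.2). A client who uses many services before the trial is likely to go on doing so. There are only 7 clinics per arm, matched on size and organisational motivation (section 4.2) and not on client severity or service use. A difference in prior service use between the arms is therefore likely to appear partly in C and to be read as a cost or a saving of ATTOC. Clients are recruited after their clinic's arm is known, so the difference could be systematic as well as due to chance.

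At stake is whether a secondary aim with a formal hypothesis test turns on which arm drew the costlier clinics, and whether the interval behind that test has its stated coverage.

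**Working it through.** **Inputs from the documents.** 14 clinics, 7 per arm (4.1); about 50 clients per clinic (5.2), so 350 per arm; ICC values 0, .05, .10 and .15, given for other outcomes (7.1).

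**Assumed.** The cost ICC, taken over the same range, and the correlation r between a client's baseline and follow-up cost, taken as .3, .5 and .7 and treated as the same within and between clinics. The documents give neither. Results are in client-level cost SDs, because no cost SD is given.

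**1. The plan's own figures.** There is no power or precision figure for cost, so none can be reproduced. The Aim 1 detectable differences check the cluster layout. SD × √[2/(7m) × (1+(m−1)ICC)] × (t.975,12 + t.80,12), with SD .87 and m = 20, gives .317, .443, .540 and .623 against the stated .32, .44, .54 and .62. The Aim 1 figures thus match a calculation with a design effect and 12 degrees of freedom. The INMB paragraph mentions neither.

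**2. Chance gap in baseline cost between arms.** SD of gap = √[(2/7) × (ICC + (1−ICC)/50)]. At ICC .05: (2/7) × (.05 + .019) = .0197, root .140. The part carried into an unadjusted C is r times the gap.

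**3. Printed against clustered SE.** The ordinary formula gives √(2/350) = .076. The clustered SE is larger by √DEFF, with DEFF = 1 + 49 × ICC. Coverage of a nominal 95% interval for C that uses the ordinary SE is 2Φ(1.96/√DEFF) − 1.

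| Cost ICC | SD of chance gap | P(gap beyond ±.25 SD) | One-SD gap carried into C, r = .3 / .5 / .7 | √DEFF | Coverage of printed 95% interval |
|---|---|---|---|---|---|
| 0 | .076 | .001 | .023 / .038 / .053 | 1.00 | 95% |
| .05 | .140 | .075 | .042 / .070 / .098 | 1.86 | 71% |
| .10 | .184 | .173 | .055 / .092 / .129 | 2.43 | 58% |
| .15 | .218 | .252 | .066 / .109 / .153 | 2.89 | 50% |

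With 15% loss (42.5 per clinic) the gap SDs at ICC .05, .10 and .15 are .144, .186 and .220, and the coverages 74%, 61% and 53%.

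**4. Gain from adjustment, clustering handled either way.** The SE of C is multiplied by √(1−r²): .954, .866 and .714 for r = .3, .5 and .7, a cut of about 5%, 13% and 29%. If C supplies half of the INMB variance (covariance ignored), the INMB factor is √(1 − .5r²) = .977, .935 and .869. If it supplies one tenth, the factors are .995, .987 and .975.

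**5. Adjusted clustered SE against the printed SE.** The ratio is √[DEFF × (1−r²)]. At ICC .05 it is 1.77, 1.61 and 1.33 for r = .3, .5 and .7; at ICC .15 it is 2.76, 2.50 and 2.06. It falls below 1 only if 49 × ICC < 1/(1−r²) − 1, that is, if ICC is below .0989/49 = .002, .333/49 = .007 or .961/49 = .020.

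**The case against.** **Adjustment is unspecified, not excluded.** Section 7.2 would let a variable related to arm in as a covariate, and section 6.1.1 expects baseline differences among UC sites to be controlled. This stands as a limit on the claim. But the section 7.2 clause is an optional screen at p < .10 that does not name cost, the section 6.1.1 sentence concerns UC sites, and neither is carried into the INMB formula.

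**Chance imbalance is imprecision, not bias.** Under sound randomisation, a correctly clustered interval already allows for it. That also stands. Adjustment is then a gain in precision, plus some protection if recruitment after allocation makes the arms differ.

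**The reach is limited.** The deciding outcome is cost per life-year saved, which uses simulated lifetime mortality and costs. Baseline cost informs only the client costs observed in the trial; ATTOC delivery cost has no baseline counterpart. The gain in the INMB is therefore smaller than the gain in C.

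**Stronger readings that the documents do not support.** A reader might infer that:
- *The INMB interval is needlessly wide.* Against the printed formula the opposite is likely: at ICC .05 the printed SE is .076, and the adjusted clustered SE is .122 (r = .5) or .100 (r = .7). The saving exists only against a clustered unadjusted analysis, which would apply if the mixed-model statement in section 7.2 were read into the INMB.
- *Baseline costs are certainly in hand.* Only the schedule table says so; sections 6.1.1 and 6.2.5 do not.
- *The effect term is immune because every client smokes at entry.* Smoking history and nicotine dependence are measured at baseline and could be imbalanced too.
- *A dollar size can be attached.* The documents give no cost SD, so any such figure would only reflect the SD chosen.

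**Conclusion.** The point holds as a specification gap in a secondary aim. As written, C takes no account of a baseline cost that the schedule table marks for collection, and the INMB standard error takes no account of clinics.

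At an assumed cost ICC of .05 to .15, the chance gap in baseline cost has an SD of about 0.14 to 0.22 client-level SDs. Baseline adjustment would cut the SE of C by about 5% to 29% for r of .3 to .7, relative to a clustered unadjusted analysis, and the SE of the INMB by less.

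The larger fault in the printed interval is the missing clustering. It makes the interval for C too narrow by a factor of 1.86 to 2.89 over that ICC range. Adding baseline cost without the clinic term would narrow it further, so the two changes belong together.

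**What to change.** In section 7.2.1:
1. Replace the raw difference and ordinary SE with a net-benefit (or cost) regression on arm and the client's own baseline cost. Include the clinic random effect that section 7.2 calls for and small-sample degrees of freedom (14 clinics less 2 arms = 12, fewer with clinic-level covariates). Take the INMB and its interval from the arm coefficient.
2. Apply the adjustment to the observed within-trial client costs, before the lifetime projection, and say how ATTOC delivery cost and the projected terms are then added.
3. Name baseline cost as a covariate in advance, not subject to the p < .10 screen, and report the unadjusted clustered INMB alongside.

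Reconcile the schedule table with sections 6.1.1 and 6.2.5, so that baseline cost collection is confirmed with a defined look-back period. If the table mark proves to be the error, the covariate does not exist without new collection; the clinic term and degrees of freedom should go in regardless.

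The cost is a few sentences and one regression, if baseline costs are collected as the table shows. The downside is an interval that may be wider than the printed formula would give.
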